Protocol Title

Respiratory virus infections in acutely hospitalized adult patients with pulmonary and extrapulmonary complications

Principal Investigator

[name]

MBBS, FRCPath, FHKCPath, FRCP (Edin), MD

Date: 4th January 2019
Version: 20190104

Table of content

Section	Content	Page number
1	Protocol synopsis	3
2	Background and rationale	4
2.1	Background of respiratory virus infection	4
2.2	Study rationale	4
3	Study Design	5
3.1	Study objectives	5
3.2	Study design and organization	5
3.2.1	Overall study design	5
3.3	Outcome measurements	6
3.3.1	Primary outcome measurement	6
3.3.2	Secondary outcome measurements	6
3.4	Informed consent	6
3.5	Confidentiality of data	6
3.6	Archive of data	7
4	Selection and enrollment of participants	7
4.1	Selection of study population at in-patient	7
4.11	Inclusion criteria	7
4.12	Exclusion criteria	7
4.2	Selection of study population at out-patient	7
4.2.1	Inclusion criteria	7
4.2.2	Exclusion criteria	7
4.3	Study enrollment procedures	8
5	Study procedures	8
5.1	Schedule of evaluations	8
5.1.1	Participants at acute medical ward (in-patients)	8
5.1.2	Participants at the out-patient clinic	8
5.2	Assessment and clinical data collection	8
5.3	Detection of respiratory viruses	9
5.3.1	Specimen collection	9
5.3.2	Molecular testing of respiratory viruses	9
5.4	Healthcare utilization of respiratory virus infection	9
6	Statistical methods	10
6.1	Sample size	10
6.2	Analysis of study	10
7	Study team and study site	11
7.1	Study team	11
7.2	Study site	11
8	References	11

1. PROTOCOL SYNOPSIS:

Protocol title	Respiratory virus infections in acutely hospitalized adult patients with pulmonary and extrapulmonary complications
Hypothesis	The incidence of respiratory virus infection were underestimated
Primary objective	To determine the incidence and adjusted population attributable fraction of respiratory virus infection among patients with pulmonary and extrapulmonary complications
Study participants	1. Adult hospitalized patients admitted to the acute medical ward of Queen Mary Hospital 2. Adult out-patients of Queen Mary Hospital
Study design	This is a prospective cohort study involving hospitalized adult patients admitted to the acute medical ward of Queen Mary Hospital, an acute care university-affiliated hospital with 1,700 beds in Hong Kong. Consecutive patients will be screened for eligibility based on inclusion and exclusion criteria. Written informed consent will be obtained from all study participants. Saliva specimens will be collected from study participants, and will be tested for respiratory viruses by a multiplex PCR panel. Patients' demographics, underlying diseases, and outcome measures will be collected. The crude incidence will be assessed. Adjusted population attributable fraction will be calculated by adjusting the crude incidence of acutely hospitalized adult patients with the background rate among adult out-patients.
Primary outcome	Incidence of respiratory viruses
Secondary outcome	1. Length of hospital stay 2. Length of stay in general medical ward 3. Length of stay in high dependency unit 4. Length of stay in intensive care unit 5. Proportion of patients requiring oxygen supplementation 6. Proportion of patients requiring positive pressure ventilation 7. Proportion of patients requiring intubation 8. Proportion of patients admitted to intensive care unit 9. Proportion of patients admitted to coronary care unit 10. Proportion of patients admitted to high dependency unit 11. Proportion of patients who die during hospitalization 12. Initial blood test results on admission 13. Radiological investigation results 14. Microbiological investigations results
Data analysis	The fraction of hospitalization that can be attributed by a particular respiratory pathogen will be calculated using adjusted population attributable fraction.

	Continuous variables and categorical variables will be compared using Mann Whitney U test and Fisher's exact test, respectively. A P value of <0.05 with two sided testing will be considered statistically significant. Statistical test will be performed using SPSS 23.0.0.
--	---

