2. BACKGROUND AND RATIONALE

2.1. Background and study rationale

Respiratory viruses cause severe infections, and contribute to a substantial number of hospitalizations, admission to intensive care units and deaths (1). Many hospitalizations due to respiratory virus infection are related to pneumonia or exacerbation of chronic lung disease. In addition, many hospitalizations are related to extrapulmonary complications, such as acute coronary syndrome or stroke (2).

Previous studies have reported the incidence of respiratory viruses among patients with pulmonary complications (3), or the association of respiratory viruses with acute coronary syndrome or stroke (4). However, there are several problems associated with these studies. First, many of these studies are retrospective in nature, and therefore testing was only performed in selected patients with respiratory symptoms. Hence, many patients without respiratory symptoms were not recruited. Second, respiratory virus can be detected in some asymptomatic individuals. Therefore, the presence of respiratory virus may be an incidental finding rather than the cause of the complication. Third, many studies only focus on a few respiratory viruses, especially on influenza virus.

This study aims to address these issues. We propose to conduct a prospective cohort study. We will recruit hospitalized adult patients with exacerbation of underlying lung disease, acute coronary syndrome or stroke. As controls, we will recruit outpatients follow-up for chronic heart disease, chronic lung disease or neurological conditions. We will collect saliva from study participants and perform respiratory virus testing using a multiplex PCR panel. Our previous studies have shown that there is a high concordance between results from respiratory virus testing on saliva and nasopharyngeal specimens (5, 6).

Our study will provide accurate data on the epidemiology of respiratory viruses in pulmonary and extrapulmonary complications. These data are important for clinicians, public health practitioners and scientists.

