3.2 Study design and organization

3.2.1 Overall study design

This is a prospective cohort study involving hospitalized adult patients admitted to the acute medical ward of Queen Mary Hospital, an acute care university-affiliated hospital with 1,700 beds in Hong Kong. Patients will be screened for eligibility based on inclusion and exclusion criteria. Written informed consent will be obtained from all study participants. Saliva specimens will be collected from study participants, and will be tested for respiratory viruses using a multiplex PCR panel. Patients' demographics, underlying diseases, and outcome measures will be collected.

Since respiratory viruses can be detected in asymptomatic adults, we will also recruit outpatients followed up for a chronic condition to determine the frequency of respiratory viruses among these patients without any acute symptoms requiring hospitalization. We will adjust the crude incidence from this background rate.

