3.3 Outcome measurements

3.3.1 Primary outcome measurement

1. Incidence of respiratory viruses

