3.3.2 Secondary outcome measurements

1. Length of hospital stay
2. Length of stay in general medical ward
3. Length of stay in high dependency unit
4. Length of stay in intensive care unit
5. Proportion of patients requiring oxygen supplementation
6. Proportion of patients requiring positive pressure ventilation
7. Proportion of patients requiring intubation
8. Proportion of patients admitted to intensive care unit
9. Proportion of patients admitted to coronary care unit
10. Proportion of patients admitted to high dependency unit
11. Proportion of patients who die during hospitalization
12. Initial blood test results on admission
13. Radiological investigation results
14. Microbiological investigations results

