4.1.2 Exclusion criteria

1. Admitted to any hospitals in the past 14 days
2. Respiratory virus testing performed in the past 14 days
3. Antiviral against respiratory virus given within the past 14 days
4. Not sufficient saliva

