6.2 Analysis of the study

Crude incidence of each respiratory virus and overall respiratory virus infection among hospitalized patients and out-patients will be estimated. To adjust for the background rate of respiratory virus detection among out-patients, we will calculate adjusted population attributable fraction (aPAF) as described previously (22). Conceptually, aPAF represents the fraction of hospitalization that can be attributed to a particular pathogen. Death rate of each detected respiratory virus and overall respiratory virus infection among patients in the acute medical wards will be estimated.

For symptomatology of respiratory viruses, frequencies and proportions of respiratory and non-respiratory symptoms for each respiratory virus and overall respiratory virus infection will be calculated.

Statistical test will be performed using SPSS version 23.0. A *P* value of <0.05 with two-sided testing will be considered statistically significant.

7. STUDY TEAM and STUDY SITE

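### The only stated hypothesis, that incidence was underestimated, names no reference, and section 6.2 plans no comparison that could support or refute it

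*Combined protocol and SAP*

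**What the plan says.** All references are to the combined protocol and SAP.

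- **Hypothesis (section 1, synopsis).** "The incidence of respiratory virus infection were underestimated". No reference rate, source or setting is given.
- **Rationale (section 2.1).** Earlier studies are criticised because "testing was only performed in selected patients with respiratory symptoms", because some detections are incidental, and because many studies covered few viruses. No rate from them is quoted.
- **Primary objective (section 1).** "To determine the incidence and adjusted population attributable fraction of respiratory virus infection among patients with pulmonary and extrapulmonary complications". The primary outcome in section 3.3.1 is "Incidence of respiratory viruses".
- **Out-patients (section 3.2.1).** Their role is to supply a background rate: "We will adjust the crude incidence from this background rate".
- **Analysis (section 6.2).** "Crude incidence of each respiratory virus and overall respiratory virus infection among hospitalized patients and out-patients will be estimated". The aPAF, death rates by virus, and symptom proportions by virus follow.
- **Data collected (sections 3.3.2, 5.1.1 and 5.2).** "Microbiological investigations results" are a secondary outcome and are extracted for the admission. Symptoms come from the enrolment questionnaire.
- **In-patient eligibility (sections 4.1.1 and 4.1.2).** Patients enter through the emergency department and are recruited within 24 hours of hospitalization. Exclusion 2 is "Respiratory virus testing performed in the past 14 days", with no exception for the index presentation.

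**The concern.** A claim of underestimation needs something to be measured against. The study's one comparison group answers a different question: how much of the in-patient detection exceeds what is found in people without acute illness. That comparison serves attribution. It cannot show that an earlier or routine estimate was too low, and removing incidental detections lowers the crude figure.

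If the plan is followed exactly, any conclusion that incidence had been underestimated would rest on an informal comparison with a reference chosen after the results are known.

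Exclusion 2 matters for a second reason. If patients swabbed on arrival are excluded, the enrolled in-patients are a selected group with respect to the primary outcome.

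**Working it through.** **1. Tracing the hypothesis through the plan.**

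| Step | Content | Reference for the hypothesis? |
|---|---|---|
| Objectives (3.1) | Estimate crude incidence and aPAF | None |
| Primary outcome (3.3.1) | One estimated quantity | None |
| Sample size (6.1) | 100 + 100, set by budget | None |
| Analysis (6.2) | Proportions by group, aPAF, deaths, symptoms | Out-patients, for background only |
| Tests (synopsis) | Mann-Whitney U, Fisher's exact | Groups to be compared not named |

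The sample size has no power or precision calculation behind it, so there is no stated figure to reproduce. All rates and counts below are assumptions.

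**2. What the planned estimate delivers.** The exact (Clopper-Pearson) 95% interval for x of n runs from the 2.5% quantile of Beta(x, n−x+1) to the 97.5% quantile of Beta(x+1, n−x). With n = 100 in-patients:

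- 10 positive: 4.9% to 17.6%
- 20 positive: 12.7% to 29.2%
- 30 positive: 21.2% to 40.0%

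Without a reference value, none of these intervals bears on underestimation.

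**3. What the out-patient contrast delivers.** By the normal approximation with 100 per group and two-sided 0.05, power is 90% for 20% against 5%, and 51% for 20% against 10%. This is power to show excess over background, not under-ascertainment.

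**4. What a routine-care contrast would deliver.** Suppose 20 of 100 in-patients are PCR-positive. The missed share is (tested negative + not tested) / PCR-positive.

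- 14 of 20 missed: 70%, exact 95% CI 45.7% to 88.1%
- 8 of 20 missed: 40%, exact 95% CI 19.1% to 63.9%

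A McNemar test adds little. If untested patients count as not detected and there are no routine-only positives, every discordant pair runs one way and p = 2 × 0.5^d for d missed patients. Five missed gives 0.0625 and six gives 0.031, so the test only asks whether at least six were missed. The chance of six or more among 100 in-patients is 38%, 82% or 94% if routine care misses 5%, 8% or 10% of all in-patients.

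Some missed detections would be incidental. At an out-patient rate of 5% or 10%, about 100 × 0.05 = 5 or 100 × 0.10 = 10 of the 20 detections would be expected from background alone.

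**5. What a fixed external reference would deliver.** Using an exact one-sample test with 100 in-patients and reference rates of 5%, 10%, 15% and 20%, power is 90%, 81%, 71% and 62% if the true rate is 10 points higher. It is 42%, 33%, 26% and 21% if the true rate is 5 points higher.

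**6. Effect of exclusion 2.** Let a fraction t of otherwise eligible in-patients be tested on arrival before recruitment, with positivity pT, and let the rest have positivity pU. The full group has t·pT + (1−t)·pU, but the study would estimate pU. The bias is −t(pT − pU), which is downward if those tested are more often positive. The documents give neither t nor pT, so its size is unknown.

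**The case against.** The strongest reply is that the hypothesis is one line of the synopsis. The objectives and primary outcome are estimation, and section 6.2 delivers both the crude incidence and the aPAF. This stands: the missing reference biases none of these estimates, and rewording one line would remove the mismatch.

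Other points limit how far the concern can be taken:

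- A reader might infer that symptoms are never set against PCR results. Section 6.2 does plan symptom proportions for each virus and overall, which bears on the section 2.1 complaint. What is missing is an explicit count of PCR-positive in-patients with no respiratory symptom at all; frequencies of single symptoms do not give it.
- A reader might infer that routine care at this hospital is the one correct reference. Section 2.1 speaks of earlier studies. Routine detection in the same patients is one reasonable reading; a named published rate is another.
- A reader might infer that exclusion 2 removes everyone whom routine care tests. It removes only those tested before recruitment; tests ordered later in the admission remain. Exclusion 1, read equally literally, would bar every in-patient because of the current admission, so the sponsor may well mean the look-back to end at presentation. The text does not say so, and screening staff could apply exclusion 2 as written.
- A reader might infer that every data item is already in hand. Section 5.2 lists microbiological results on admission, but does not name virus tests or record whether one was ordered.

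**Conclusion.** The point holds. The only stated hypothesis has no reference, and no analysis in section 6.2 could support or refute it. The out-patient group does not fill the gap. The estimation objectives are unaffected, so this is a change the sponsor should make, not a flaw that invalidates the study.

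A contrast with routine detection is feasible at 100 in-patients but imprecise: an interval of 46% to 88% for 14 of 20 missed, and 19% to 64% for 8 of 20. These figures rest on an assumed 20% positivity and assumed missed counts. It would be too strong to say that small p-values from such a table prove under-ascertainment, because the discordance is almost one-directional by construction.

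The exclusion 2 problem rests on a literal reading. Its direction depends on whether patients tested on arrival are more often positive, and its size cannot be derived from the documents.

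**What to change.** 1. **Section 6.2, routine-care contrast.** In the in-patients, cross-tabulate study saliva PCR (positive, negative) against routine virus testing in the index admission (detected, tested negative, not tested). Report the proportion of PCR-positive patients not detected by routine care with an exact 95% CI, and show how many were untested and how many tested negative. No McNemar test is needed. Read the missed detections alongside the out-patient background rate.
2. **Section 6.2, symptoms.** From the symptom table already planned, report explicitly the proportion of PCR-positive in-patients with no respiratory symptoms, with an exact 95% CI.
3. **Section 4.1.2.** Limit exclusion 2 to tests done before the index presentation. The out-patient criterion needs no change. Section 4.3 already records reasons for ineligibility, so the number excluded on this ground can be reported.
4. **Section 5.2.** State that the extraction covers whether a routine virus test was ordered in the index admission, when, and its result.
5. **Alternative to item 1.** If the sponsor does not want that contrast, restate the hypothesis as descriptive, preferably with a precision target.

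The cost is a short paragraph in 6.2, one eligibility clause, and a small extension or clarification of the record extraction. No new visit, specimen or assay is needed. The downsides are a minor eligibility clarification, which would need to be handled as such, and the wide intervals shown above.

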2. BACKGROUND AND RATIONALE

2.1. Background and study rationale

Respiratory viruses cause severe infections, and contribute to a substantial number of hospitalizations, admission to intensive care units and deaths (1). Many hospitalizations due to respiratory virus infection are related to pneumonia or exacerbation of chronic lung disease. In addition, many hospitalizations are related to extrapulmonary complications, such as acute coronary syndrome or stroke (2).

Previous studies have reported the incidence of respiratory viruses among patients with pulmonary complications (3), or the association of respiratory viruses with acute coronary syndrome or stroke (4). However, there are several problems associated with these studies. First, many of these studies are retrospective in nature, and therefore testing was only performed in selected patients with respiratory symptoms. Hence, many patients without respiratory symptoms were not recruited. Second, respiratory virus can be detected in some asymptomatic individuals. Therefore, the presence of respiratory virus may be an incidental finding rather than the cause of the complication. Third, many studies only focus on a few respiratory viruses, especially on influenza virus.

This study aims to address these issues. We propose to conduct a prospective cohort study. We will recruit hospitalized adult patients with exacerbation of underlying lung disease, acute coronary syndrome or stroke. As controls, we will recruit outpatients follow-up for chronic heart disease, chronic lung disease or neurological conditions. We will collect saliva from study participants and perform respiratory virus testing using a multiplex PCR panel. Our previous studies have shown that there is a high concordance between results from respiratory virus testing on saliva and nasopharyngeal specimens (5, 6).

Our study will provide accurate data on the epidemiology of respiratory viruses in pulmonary and extrapulmonary complications. These data are important for clinicians, public health practitioners and scientists.

3. STUDY DESIGN

3.1. Study objectives

1. To determine the crude incidence of respiratory virus infection among patients with exacerbation of chronic lung disease, acute coronary syndrome or stroke
2. To determine the adjusted population attributable fraction of respiratory virus infection among patients with exacerbation of chronic lung disease, acute coronary syndrome or stroke

3.2 Study design and organization

3.2.1 Overall study design

This is a prospective cohort study involving hospitalized adult patients admitted to the acute medical ward of Queen Mary Hospital, an acute care university-affiliated hospital with 1,700 beds in Hong Kong. Patients will be screened for eligibility based on inclusion and exclusion criteria. Written informed consent will be obtained from all study participants. Saliva specimens will be collected from study participants, and will be tested for respiratory viruses using a multiplex PCR panel. Patients' demographics, underlying diseases, and outcome measures will be collected.

Since respiratory viruses can be detected in asymptomatic adults, we will also recruit outpatients followed up for a chronic condition to determine the frequency of respiratory viruses among these patients without any acute symptoms requiring hospitalization. We will adjust the crude incidence from this background rate.

3.3 Outcome measurements

3.3.1 Primary outcome measurement

1. Incidence of respiratory viruses

3.3.2 Secondary outcome measurements

1. Length of hospital stay
2. Length of stay in general medical ward
3. Length of stay in high dependency unit
4. Length of stay in intensive care unit
5. Proportion of patients requiring oxygen supplementation
6. Proportion of patients requiring positive pressure ventilation
7. Proportion of patients requiring intubation
8. Proportion of patients admitted to intensive care unit
9. Proportion of patients admitted to coronary care unit
10. Proportion of patients admitted to high dependency unit
11. Proportion of patients who die during hospitalization
12. Initial blood test results on admission
13. Radiological investigation results
14. Microbiological investigations results

3.4. Informed consent

The investigator or his/her representative will explain the nature of the study to the subjects, and answer all questions by the subjects regarding this study. Prior to any study-related screening procedures being performed on the subject, the informed consent statement will be reviewed and signed and dated by the subjects and the person who administered the informed consent.

3.5 Confidentiality of data

Permission for direct access to a subject's data will be sought in writing by the investigator and from the subject as part of the informed consent procedure. This gives permission to examine, analyse, verify and reproduce any records and reports that are important to the evaluation of the study. Any party (e.g., domestic and foreign regulatory authorities, monitors and auditors) with direct access must take all reasonable precautions within the constraints of the applicable regulatory requirements to maintain the confidentiality of the subjects' identities and the Hospital Authority's proprietary

information. It is the monitor's responsibility to verify that each subject has consented, in writing, to direct access.

